9.4.2 Safety Endpoints

Safety and tolerability will be assessed by clinical review of all relevant parameters including AEs and postvaccination temperature measurements following any vaccination with V114 or Prevenar 13™.

The safety endpoints include:

- Proportion of participants with solicited injection-site AEs (swelling, redness/erythema, tenderness/pain, and hard lump/induration) from Day 1 through Day 14 following any vaccination with V114 or Prevenar 13™
- Proportion of participants with solicited systemic AEs (irritability, drowsiness/somnolence, hives or welts/urticaria, and appetite loss/decreased appetite) from Day 1 through Day 14 following any vaccination with V114 or Prevenar 13™
- Proportions of participants with the broad AE categories consisting of any AE and a vaccine-related AE from Day 1 through Day 14 following any vaccination with V114 or Prevenar 13™
- Proportions of participants with an SAE, a vaccine-related SAE, and discontinuation due to an AE, and death from Day 1 (day of Dose 1) through completion of study participation
- Participants body temperature measured from Day 1 (day of vaccination) through Day 7 following any vaccination with V114 or Prevenar 13™

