Visit Window:	2 months of age to 1 day prior to 7 months of age	28 to 56 days after Dose 1	28 to 56 days after Dose 2	28 to 42 days after Dose 3	12 months of age to 1 day prior to 16 months of age	28 to 42 days after Dose 4	Visit 2 (Dose 2) and Visit 3 (Dose 3) could be later than the upper limit of visit window but Visit 3 (Dose 3) must be before 12 months of age and at least 60 days interval is needed between Visit 3 (Dose 3) and Visit 5 (Dose 4).
30-Minute Postvaccination Observation Period	X	X	X		X		To be performed by blinded study site personnel only.
AE Monitoring	X	X	X	X	X	X	Nonserious AEs are to be reported from Days 1 through 14 following each vaccination. SAEs, deaths and medical device incidents are to be reported throughout the duration of an individual's study participation. See Section 8.4, 10.3 and 10.4 for details.
Immunogenicity Procedures							
Collect Blood (Serum) for Immunogenicity Assays				X	X	X	Blood samples must be collected before vaccination where applicable.
Future Biomedical Research							
Collect Buccal Swabs for FBR	X						Buccal swab DNA samples for analysis should be obtained prior to vaccination at Visit 1, on randomized and FBR consented participants only.

AE = adverse event; DNA = deoxyribonucleic acid; VRC = Vaccination Report Card; FBR = Future Biomedical Research; SAE = serious adverse event

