6.4 Study Intervention Compliance

Interruptions from the protocol-specified plan for V114 and Prevenar 13™ vaccination as indicated in Section 1.3 require consultation between the investigator and the Sponsor and written documentation of the collaborative decision on participant management.

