7 DISCONTINUATION OF STUDY INTERVENTION AND PARTICIPANT WITHDRAWAL

7.1 Discontinuation of Study Intervention

Discontinuation of study intervention does not represent withdrawal from the study.

As certain data on clinical events beyond study intervention discontinuation may be important to the study, they must be collected through the participant's last scheduled follow-up, even if the participant has discontinued study intervention. Therefore, all participants who discontinue study intervention prior to completion of the protocol-specified vaccination regimen will still continue to participate in the study as specified in Section 1.3 and Section 8.11.3.

Participants may discontinue study intervention at any time for any reason or be discontinued from the study intervention at the discretion of the investigator should any untoward effect occur. In addition, a participant may be discontinued from study intervention by the investigator or the Sponsor if study intervention is inappropriate, the study plan is violated, or for administrative and/or other safety reasons. Specific details regarding procedures to be performed at study intervention discontinuation are provided in Section 8.1.10 and Section 8.11.3.

A participant must be discontinued from study intervention but continue to be monitored in the study for any of the following reasons:

- The participant's legally acceptable representative requests to discontinue study intervention.
- The participant's treatment assignment has been unblinded by the investigator, MSD subsidiary, or through the emergency unblinding call center.
- The participant has a medical condition or personal circumstance which, in the opinion of the investigator and/or Sponsor, placed the participant at unnecessary risk from continued administration of study intervention.

For participants who are discontinued from study intervention but continue to be monitored in the study, see Section 1.3 and Section 8.11.3 for those procedures to be completed at each specified visit.

Discontinuation from study intervention is "permanent." Once a participant is discontinued, he/she shall not be allowed to restart study intervention.

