8.3.3 Safety Assessment and Use of the VRC

All participants will be observed for 30 minutes after each vaccination for any immediate reactions. If any immediate AEs are observed during this period, the time at which the event occurred within this timeframe, as well as the event itself, any concomitant medications that were administered, and resolution of the event, must be recorded on the appropriate eCRF.

Participant's parent/guardian will use the VRC (Section 8.1.9) to document the following information:

- Axillary temperatures measured Day 1 (day of vaccination) through Day 7 following each vaccination; Day 8 through Day 14 following each vaccination if fever is suspected
- Solicited injection-site AEs (swelling, redness, pain or tenderness, and hard lump) Day 1 through Day 14 postvaccination
- Solicited systemic AEs (irritability, drowsiness, appetite lost, and hives or welts) Day 1 through Day 14 postvaccination
- Any other unsolicited injection-site or systemic AEs Day 1 through Day 14 postvaccination
- Concomitant medications and non-study vaccinations Day 1 to Day 14 postvaccination

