8.4 Adverse Events, Serious Adverse Events, and Other Reportable Safety Events

The definitions of an AE or SAE, as well as the method of recording, evaluating, and assessing causality of AE and SAE and the procedures for completing and transmitting AE, SAE, and other reportable safety event reports can be found in Appendix 3.

Adverse events, SAEs, and other reportable safety events will be reported by the participant (or, when appropriate, by a caregiver, surrogate, or the participant's legally authorized representative).

The investigator and any designees are responsible for detecting, documenting, and reporting events that meet the definition of an AE or SAE as well as other reportable safety events. Investigators remain responsible for following up AEs, SAEs, and other reportable safety events for outcome according to Section 8.4.3.

The investigator, who is a qualified physician, will assess events that meet the definition of an AE or SAE as well as other reportable safety events with respect to seriousness, intensity/toxicity and causality.

8.4.1 Time Period and Frequency for Collecting AE, SAE, and Other Reportable Safety Event Information

All AEs, SAEs, and other reportable safety events that occur after the consent form is signed but before allocation/randomization must be reported by the investigator if they cause the participant to be excluded from the study, or are the result of a protocol-specified intervention, including but not limited to washout or discontinuation of usual therapy, diet, placebo, or a procedure.

From the time of allocation/randomization through 14 days (42 days for live attenuated vaccines) following the first vaccination(s) and from the time of any subsequent vaccination(s) through 14 days (42 days for live attenuated vaccines) thereafter, all AEs, SAEs, and other reportable safety events must be reported by the investigator.

Additionally, any SAE brought to the attention of an investigator at any time outside of the time period specified in the previous paragraph also must be reported immediately to the Sponsor if the event is either:

- A death that occurs prior to the participant completing the study, but outside the time period specified in the previous paragraph.

OR

- An SAE that is considered by an investigator, who is a qualified physician, to be vaccine related.

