Investigators are not obligated to actively seek AEs or SAEs or other reportable safety events in former study participants. However, if the investigator learns of any SAE, including a death, at any time after a participant has been discharged from the study, and he/she considers the event to be reasonably related to the study intervention or study participation, the investigator must promptly notify the Sponsor.

SAEs must also be reported throughout the duration of the individual's participation in the study, regardless of whether or not related to the Sponsor's product.

All initial and follow-up AEs, SAEs, and other reportable safety events will be recorded and reported to the Sponsor or designee within the time frames as indicated in [Table 2](#).

Table 2 Reporting Time Periods and Time Frames for Adverse Events and Other Reportable Safety Events

Type of Event	Reporting Time Period: Consent to Randomization/ Allocation	Reporting Time Period: Randomization/ Allocation through Protocol-specified Follow-up Period	Reporting Time Period: After the Protocol-specified Follow- up Period	Time Frame to Report Event and Follow-up Information to Sponsor:
NSAE	Report if: - due to protocol-specified intervention - causes exclusion - participant is receiving placebo run-in or other run-in treatment	Report all	Not required	Per data entry guidelines
SAE	Report if: - due to protocol-specified intervention - causes exclusion - participant is receiving placebo run-in or other run-in treatment	Report all	Report if: - drug/vaccine related. - any death until participant completion of study (Follow ongoing to outcome)	Within 24 hours of learning of event
ECI	There are no ECI for this study.			Not applicable
Cancer	Report if: - due to intervention - causes exclusion	Report all	Not required	Within 5 calendar days of learning of event
Overdose	Report if: - receiving placebo run-in or other run-in medication	Report all	Not required	Within 5 calendar days of learning of event

DILI=drug-induced liver injury; ECI=event of clinical interest; NSAE=nonserious adverse event; SAE=serious adverse event

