8.4.3 Follow-up of AE, SAE, and Other Reportable Safety Event Information

After the initial AE/SAE report, the investigator is required to proactively follow each participant at subsequent visits/contacts. All AEs, SAEs, and other reportable safety events, including cancer, and overdose will be followed until resolution, stabilization, until the event is otherwise explained, or the participant is lost to follow-up (as defined in Section 7.3). In addition, the investigator will make every attempt to follow all nonserious AEs that occur in

randomized participants for outcome. Further information on follow-up procedures is given in Appendix 3.

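### Can a nonserious adverse event that starts after Day 14 and ends vaccination be missed from the discontinuation endpoint?

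*Protocol*

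**What the plan says.** **Endpoint.** Protocol 9.4.2 and sSAP 3.4.2 use the same wording: the proportion with "discontinuation due to an AE, and death from Day 1 (day of Dose 1) through completion of study participation", listed with SAEs and vaccine-related SAEs. The preceding bullet in each list limits any AE and vaccine-related AE to Days 1 to 14. Under Protocol 9.6.2 and sSAP 3.6.2, discontinuation due to an AE is a Tier 2 endpoint with a between-group 95% CI.

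**Collection.**
- Protocol 1.3: "Nonserious AEs are to be reported from Days 1 through 14 following each vaccination".
- Protocol 8.3.3, for the Vaccination Report Card: "Any other unsolicited injection-site or systemic AEs Day 1 through Day 14 postvaccination".
- Protocol 8.4.1, after each later dose: "through 14 days (42 days for live attenuated vaccines) thereafter, all AEs, SAEs, and other reportable safety events must be reported by the investigator". The 42-day period does not apply to the study vaccines, which are conjugates.
- Protocol Table 2: reporting of nonserious AEs is not required after the protocol-specified follow-up period.
- Protocol 8.4.1, for serious events: "SAEs must also be reported throughout the duration of the individual's participation in the study, regardless of whether or not related" to the Sponsor's product.

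**Discontinuation.** Protocol 7.1: "Participants may discontinue study intervention at any time for any reason". Neither document exempts an AE from the 14-day limit because it led to discontinuation.

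**The concern.** The endpoint covers the whole of participation and its wording does not limit the AE to serious events, while the duty to report nonserious AEs lapses two weeks after each dose. An infant could develop a nonserious condition some weeks after Dose 3, have Dose 4 withheld because of it, and never have that condition reported as an AE. If the endpoint is built from AE records alone, that infant is not counted.

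The protocol foresees the situation. Section 8.1.8 requires a check for new contraindications before each dose, 8.11.2 deals with a new condition that makes the participant ineligible, and 7.1 requires discontinuation where the investigator or Sponsor judges that further vaccination carries unnecessary risk. At stake would be an undercount of a pre-specified safety endpoint that is reported with a between-group interval.

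**Working it through.** There is no planned figure to reproduce, so the check sets the rules side by side and then sizes the gap.

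**1. Which cases are covered?**

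| AE leading to discontinuation | Reported as an AE? | Basis in the protocol |
|---|---|---|
| Serious, any onset during participation | Yes | 1.3, 8.4.1 |
| Nonserious, onset Days 1 to 14, discontinuation at any later date | Yes | 1.3, 8.3.3, 8.4.1 |
| Nonserious, onset after Day 14 | Not required | Table 2 |

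The second row explains the long window. Discontinuation is a dated event, and it may come at the next visit, weeks after the AE began. A window closed at Day 14 would lose those cases. The item-by-item choice of windows in 9.4.2 supports this reading.

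**2. Would a third-row case leave a trace?** Several provisions bear on it:
- 6.4 requires consultation with the Sponsor and "written documentation of the collaborative decision on participant management" when the vaccination plan is interrupted.
- 8.11.2 asks for prompt discussion with the Sponsor about a new condition that affects eligibility.
- 8.3.1 puts clinically significant examination findings at the vaccination visits on the eCRF.
- 10.3.4 has the investigator record relevant AE information at each examination. It states no Day 14 limit, although 10.3.5 refers back to 8.4.1 for reporting times.
- 9.6.3 displays the primary reasons for discontinuation.

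None of these is a duty to report the AE. In 8.4.3, "the investigator will make every attempt to follow all nonserious AEs that occur in" randomized participants concerns follow-up to outcome and does not lengthen the initial reporting period. Taken together, the provisions make it unlikely that such a case would go unrecorded. What is unstated is whether those records feed the endpoint.

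**3. How much time lies outside the windows?** Inputs: four doses, 14 days each, participation of about 7 to 14 months (Protocol 1.1), and at least 60 days between Doses 3 and 4 (1.3). One month is taken as 30.44 days.
- Covered: 4 × 14 = 56 days.
- Participation: 7 × 30.44 = 213 days to 14 × 30.44 = 426 days.
- Share covered: 56/213 = 26% to 56/426 = 13%. Share not covered: 74% to 87%.
- Shortest uncovered stretch between Doses 3 and 4: 60 − 14 = 46 days.

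These are shares of calendar time and do not measure risk. They include the period after Dose 4, when no vaccination remains to be discontinued, and they say nothing about how often a clearly nonserious, late-onset event ends vaccination. The documents give no such rate.

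**The case for a change.** The strongest argument for a change is that one participant can alter the result. The unstratified Miettinen and Nurminen 95% interval with 330 per arm, in percentage points, is:

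| Events, one arm v the other | 95% CI |
|---|---|
| 3 v 0 | −0.25 to 2.64 |
| 4 v 0 | 0.05 to 3.08 |
| 4 v 1 | −0.60 to 2.81 |
| 5 v 1 | −0.33 to 3.23 |
| 6 v 1 | −0.07 to 3.64 |

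A missed fourth case against none would move the interval from excluding zero to including it. That arithmetic is right, but it restates the plan's own reason for its Tier 2 threshold of 4 and would hold for any binary event at this sample size. With one event in the other arm, 4, 5 and 6 events all give intervals that include zero. The table shows sensitivity at particular counts and gives no evidence that cases would be missed. Both documents also call these intervals descriptive.

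A second argument does stand: neither document states that the period means the date of discontinuation, or names the record that defines the endpoint. A third cannot be settled here. Table 2 refers to data entry guidelines for the timing of nonserious AE reports. Those guidelines are not among the documents reviewed and may or may not cover an AE recorded as the reason for stopping.

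**Conclusion.** The observation is accurate but narrow. The windows do not contradict each other once the endpoint's period is taken as the date of discontinuation. The uncovered case is a nonserious AE with onset after Day 14 that ends vaccination. The SAE definition in Protocol 10.3.2 narrows it further, because hospitalizations and important medical events count as serious and are reported throughout.

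An analyst can handle what remains by checking disposition reasons against AE records before unblinding, which is ordinary work when this endpoint is programmed. Any residual undercount cannot be quantified from the documents. It would arise under the same reporting rule in both arms, with assessors blinded, and would touch one descriptive endpoint. The primary safety endpoints (solicited AEs through Day 14 and vaccine-related SAEs), the three immunogenicity hypotheses and the power calculations do not use it.

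The conclusion rests on two assumptions: that the period refers to when discontinuation occurred, and that sites document reasons for discontinuation as 6.4 and 9.6.3 imply. On that footing the safety conclusion stays sound with the plan as written, and no change is needed.

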9.5 Analysis Populations

9.5.1 Immunogenicity Analysis Population

The PP population will serve as the primary population for the analysis of immunogenicity data in this study. The PP population consists of all randomized participants without deviations from the protocol that may substantially affect the results of the immunogenicity

endpoint(s). Potential deviations that may result in the exclusion of a participant from the PP population for all immunogenicity analyses include:

- Failure to receive primary infant series vaccination (V114 or Prevenar 13™ Doses 1, 2, and 3) as per randomization schedule
- Receipt of prohibited medication or prohibited vaccine prior to the first study vaccination

Additional potential deviations that may result in the exclusion from the PP immunogenicity analyses at a particular timepoint include:

- Failure to receive Dose 4 of V114 or Prevenar 13™ according to vaccination schedule required at the timepoint for the analysis
- Failure to receive the scheduled doses of V114 or Prevenar 13™ with the specified intervals / time window (at least 28 days between Doses 1 and 2 and between Doses 2 and 3 [for PD3 and Predose 4 analysis], 12 months to 1 day prior to 16 months of age for Dose 4 [for PD4 analyses])
- Receipt of prohibited medication or prohibited vaccine prior to a blood sample collection
- Collection of blood sample at the timepoint for the analysis outside of the pre specified window (as described in Section 1.3)

The final determination on protocol deviations, and thereby the composition of the PP population, will be made prior to the unblinding of the database.

A supportive analysis using the Full Analysis Set (FAS) population may also be performed for the primary immunogenicity endpoints. The FAS population consists of all randomized participants who received all study vaccinations required at the timepoint for the analysis and have serology result.

Participants will be included in the vaccination group to which they are randomized for the analysis of immunogenicity data.

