1.3 Schedule of Activities

Study Period	Screening/ Intervention						Notes
Visit Number:	Visit 1	Visit 2	Visit 3	Visit 4	Visit 5	Visit 6	
Scheduled Time:	Age: 2-6 months (Dose 1)	~1 month after Dose 1 (Dose 2)	~1 month after Dose 2 (Dose 3)	~1 month after Dose 3	Age: 12 to 15 months (Dose 4)	~1 month after Dose 4	See Section 8.1.10 for details on discontinuation.
Visit Window:	2 months of age to 1 day prior to 7 months of age	28 to 56 days after Dose 1	28 to 56 days after Dose 2	28 to 42 days after Dose 3	12 months of age to 1 day prior to 16 months of age	28 to 42 days after Dose 4	Months of age is calculated according to the participant's birth date.
							Visit 2 (Dose 2) and Visit 3 (Dose 3) could be later than the upper limit of visit window but Visit 3 (Dose 3) must be before 12 months of age and at least 60 days interval is needed between Visit 3 (Dose 3) and Visit 5 (Dose 4).
Administrative and General Procedures							
Screening Procedures							
Informed Consent	X						Consent must be obtained before any study procedures.
Informed Consent for Future Biomedical Research (FBR)	X						Participation in FBR is optional and consent must be obtained before collection of buccal swab DNA samples.
Assignment of Screening Number	X						
Participant Identification Card	X						
Inclusion/Exclusion Criteria	X						Review of prior medications/vaccinations, a complete physical examination, and temperature measurement are required at Visit 1 to determine eligibility.
Medical History	X						
Post-Randomization Procedures							
Assignment of Randomization Number	X						
Prior/Concomitant Medication and Non-Study Vaccination Review	X	X	X	X	X	X	

Study Period	Screening/Intervention						Notes
Visit Number:	Visit 1	Visit 2	Visit 3	Visit 4	Visit 5	Visit 6	
Scheduled Time:	Age: 2-6 months (Dose 1)	~1 month after Dose 1 (Dose 2)	~1 month after Dose 2 (Dose 3)	~1 month after Dose 3	Age: 12 to 15 months (Dose 4)	~1 month after Dose 4	See Section 8.1.10 for details on discontinuation. Months of age is calculated according to the participant's birth date.

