2.1 Study Rationale

Routine PCV immunization of children is effective in preventing vaccine serotype-specific pneumococcal disease. Despite the availability of PCVs, pneumococcal disease remains a concern as non-vaccine serotypes have gradually emerged in increasing frequency in invasive pneumococcal disease (IPD) isolates. Given the high morbidity and mortality of IPD worldwide, the evolving serotype distribution, and the value of multiple suppliers to strengthen global supply, there is a continued need to develop new PCVs with comparable immunogenicity to licensed PCVs for shared serotypes and expanded serotype coverage. V114 includes an additional 2 key serotypes compared with Prevenar 13™ and will address an unmet medical and public health need for a PCV with expanded coverage.

The purpose of this clinical study is to evaluate the safety and immunogenicity of a 4-dose schedule (3-dose primary series followed by a toddler dose) of V114 compared with Prevenar 13™. Country-specific routine immunization regimens vary by schedule and number of doses. In Japan, a 4-dose schedule, consisting of a 3-dose primary series at approximately 2, 3 and 4 months of age followed by a toddler dose at 12 to 15 months of age, is currently recommended by Japan Pediatric Society. In this study, the first dose is given at 2 to 6 months of age and 2nd and 3rd dose is given with an interval of ≥ 27 days from the prior doses.

It is generally recommended that Prevenar 13™ is to be given at the same time as other National Immunization Program (NIP) pediatric vaccines. The concomitant administration of V114 with most NIP pediatric vaccines will be allowed in this Phase 3 clinical study at the discretion of investigators.

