4 STUDY DESIGN

4.1 Overall Design

This is a randomized, active comparator-controlled, parallel-group, multi-site, double-blind, study of V114 in healthy Japanese infants enrolled at 2 to 6 months of age. Approximately 660 infants will be randomly assigned, in 1:1 ratio with stratification into 3 categories by age category (2 months, 3 months and 4 to 6 months of age), to receive either V114 (330 participants) or Prevenar 13™ (330 participants).

A 0.5 mL subcutaneous dose of V114 or Prevenar 13™ will be administered (blinded) to healthy Japanese infants with the 1st dose given at 2 to 6 months of age and 2nd and 3rd dose is given at an interval of ≥27 days from the prior dose. Then, the 4th dose at 12 to 15 months of age is administered.

Participants will be followed for injection-site and systemic AEs through Day 14 following each vaccination with V114 or Prevenar 13™. Information for SAEs and deaths, regardless of whether the events are considered vaccine-related by the investigator, will be collected from the time consent is signed through completion of participation in the study.

Blood samples for immunogenicity assays will be collected at 3 timepoints: (1) 30 days after the completion of the 3-dose primary series (PD3), (2) immediately before receipt of Dose 4 (Predose 4), and (3) 30 days after Dose 4 (PD4).

After completion of immunogenicity testing to evaluate the study objectives and hypotheses, serum samples will be stored to conduct any additional study-related testing as required by regulatory agencies or the Sponsor. For randomized study participants who provided consent for Future Biomedical Research, leftover sera from the study may be used for other purposes

such as the development and/or validation of pneumococcal assays after completion of all study-related immunogenicity testing.

Specific procedures to be performed during the study, as well as their prescribed times and associated visit windows, are outlined in the SoA in Section 1.3. Details of each procedure are provided in Section 8.

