14. *Has received other licensed non-live vaccines within 14 days before receipt of study vaccines or is scheduled to receive any licensed non-live vaccine within 14 days following receipt of study vaccines. **Exception:** Inactivated influenza vaccine may be administered but must be given at least 7 days before receipt of study vaccines or at least 15 days after receipt of study vaccines.
15. *Has received a licensed live vaccine within 28 days before receipt of study vaccines or is scheduled to receive any live vaccine within 14 days following receipt of study vaccines.
16. Has received a blood transfusion or blood products, including immunoglobulins.

Prior/Concurrent Clinical Study Experience

17. Has participated in another clinical study of an investigational product before the beginning or anytime during the duration of the current clinical study. Participants enrolled in observational studies may be included; these will be reviewed on a case-by-case basis for approval by the Sponsor.

Other Exclusions

18. Has any other reason that, in the opinion of the investigator, may interfere with the evaluation required by the study. Reasons may include, but are not limited to, being unable to keep appointments or planning to relocate far away during the study.
19. Is or has an immediate family member (eg, spouse, parent/legal guardian, sibling, or child) who is investigational site or Sponsor staff directly involved with this study.

For items with an asterisk (*), if the participant meets these exclusion criteria, Visit 1 may be rescheduled for a time when these criteria are not met.

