6.5 Concomitant Therapy

Medications or vaccinations specifically prohibited in the exclusion criteria are not allowed during time periods specified by this protocol for that medication or vaccination (see Section 5.2 for details). If there is a clinical indication for any medications or vaccinations specifically prohibited, discontinuation from study intervention may be required. The investigator should discuss any questions regarding this with the Sponsor Clinical Director. The final decision on any supportive therapy or vaccination rests with the investigator and/or the participant's primary physician. However, the decision to continue the participant on study intervention requires the mutual agreement of the investigator, the Sponsor, and the participant's legally acceptable representative.

If a medical condition requires the use of a prohibitive steroid regimen, immunoglobulin, blood, or blood products during a participant's participation in this study, one of the individuals listed on the Sponsor Contact Information page must be notified as soon as possible. Any concurrent medication or medical treatment must be recorded on the appropriate electronic Case Report Form (eCRF). It is important to record the use of any analgesic or antipyretic medication that occurs on the day of vaccination on the VRC and appropriate eCRF.

During influenza season, it is anticipated that participants 6 months of age and older may be given inactivated influenza vaccine. Inactivated influenza vaccine should be administered either 7 days prior to or 15 days after the administration of V114 or Prevenar 13™. The influenza vaccine should not be administered at the same time as V114 or Prevenar 13™.

Other non-study pediatric vaccines (oral or injectable) including NIP vaccines can be administered on the same time as V114 or Prevenar 13™. Rotavirus vaccine administered orally is recommended to be given before V114 or Prevenar 13™ and other injectable concomitant vaccines. Other pediatric injectable vaccines are administered after V114 or

Prevenar 13™ and in a separate limb. When the non-live or live vaccine is administered on a different day from V114 or Prevenar 13™, these vaccines can be administered from 15 days after V114 or Prevenar 13™. These vaccines should be recorded on the appropriate eCRF.

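### Do the per-protocol rules remove infants who were vaccinated as other sections of the protocol allow?

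*Protocol*

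**What the plan says.** **Dose interval.** Section 2.1 says the "2nd and 3rd dose is given with an interval of ≥ 27 days from the prior doses", and Section 4.1 says the "2nd and 3rd dose is given at an interval of ≥27 days from the prior dose". The Schedule of Activities (Section 1.3) sets Visit 2 at "28 to 56 days after Dose 1" and uses the same window, counted from Dose 2, for Visit 3. A note there lets both visits run later than the upper limit. Protocol 9.5.1 and sSAP 3.5.1 use the 28-day figure: "at least 28 days between Doses 1 and 2 and between Doses 2 and 3 [for PD3 and Predose 4 analysis".

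**Other vaccines.** Exclusion criterion 14 bars non-live vaccines in the 14 days before a study dose, with a 7-day limit for inactivated influenza vaccine. Criterion 15 covers an infant who "Has received a licensed live vaccine within 28 days before receipt of study vaccines". Both also bar vaccines in the 14 days after a study dose. Section 6.5 first states that vaccines barred by the exclusion criteria stay barred for the periods given, and refers to 5.2. It then says of live or non-live vaccines given on another day that "these vaccines can be administered from 15 days after V114 or Prevenar 13™". It also permits vaccination at the same visit.

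**Force of the PP rules.** The timepoint-specific list in 9.5.1 opens: "Additional potential deviations that may result in the exclusion from the PP immunogenicity analyses at a particular timepoint include". Receipt of a prohibited vaccine before a blood sample is on that list. PP membership is fixed before the database is unblinded.

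**The concern.** Read section by section, the protocol seems to penalise infants who were handled correctly. A second dose given 27 days after the first satisfies 2.1 and 4.1 but is one day short of the PP rule. A non-live vaccine given 15 days after Dose 1 fits the sentence in 6.5. If Dose 2 then falls on day 28, that vaccine was given only 13 days before it, inside the 14-day window of criterion 14, and so becomes a prohibited vaccine for PP purposes.

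The PP population carries the primary analysis, and the stated power of about 83% assumes 300 PP participants per arm out of 330 randomized. If infants were lost this way, or kept in some cases and dropped in others, the trial could lose power and the make-up of its primary population would be hard to defend.

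**Working it through.** **1. The interval passages side by side**

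| Place | Minimum interval |
|---|---|
| Protocol 2.1 (rationale) | 27 days |
| Protocol 4.1 (design overview) | 27 days |
| Protocol 1.3 (Schedule of Activities) | 28 days |
| Protocol 9.5.1 and sSAP 3.5.1 (PP rule) | 28 days |

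Section 4.1 itself says that "prescribed times and associated visit windows, are outlined in the SoA in Section 1.3". Section 8 makes adherence to the schedule a requirement, and Section 8.1.8.1 says the vaccines are administered according to Section 1.3. A dose at a date difference of 27 days is therefore already outside the visit window; the PP rule adds no new restriction. An interval of 28 days or more also satisfies 27 days or more, so a site that follows the schedule breaches nothing. The documents do not say whether 27 days means clear days or a date difference. If clear days were meant, the two figures would agree.

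**2. Whether 5.2 and 6.5 can both be met**

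Count days from the previous study dose and let *g* be the day of the next one. The 6.5 sentence covers days 15 to *g* − 1. Criterion 14 requires *g* − *d* > 14 for a non-live vaccine on day *d*; criterion 15 requires *g* − *d* > 28 for a live one.

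- *g* = 28: days 15 to 27 lie 13 to 1 days before the next dose. None is allowed under criterion 14 or 15, influenza vaccine aside.
- Earliest *g* that clears a day-15 non-live vaccine: 15 + 14 + 1 = day 30.
- Earliest *g* that clears a day-15 live vaccine: 15 + 28 + 1 = day 44.
- *g* = 56: non-live vaccines fit on days 15 to 41 and live vaccines on days 15 to 27.

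If exactly 14 or 28 days is acceptable, days 30 and 44 become 29 and 43. Inactivated influenza vaccine needs only 7 days, so 13 days meets its limit. The rules are thus tight at 28-day spacing and compatible at longer spacings, which Section 1.3 permits. Same-visit vaccination avoids the question of separate days.

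**3. What a loss of PP participants would cost**

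Inputs: Table 5 response rates, with 23F as comparator for the two unique serotypes as its footnote states; margin −0.1; 1-sided α 0.025; log-scale SD 1.1 and true ratio 1.0 for the GMC hypothesis (H3).

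For each serotype, power is the binomial probability of all outcomes with Z > 1.96, where

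Z = (x₁/n − x₂/n + 0.1) / √V, V = [p̃₁(1 − p̃₁) + p̃₂(1 − p̃₂)]/n × 2n/(2n − 1),

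and p̃₁, p̃₂ are the maximum-likelihood rates restricted to a difference of −0.1 (unstratified Miettinen-Nurminen). Joint power is the product over 15 serotypes, assuming independence.

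At n = 300 the serotypes with power visibly below 1 are 6A 0.93676, 6B 0.98896, 33F 0.90111, 5 0.99981 and 23F 0.99993:

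0.93676 × 0.98896 × 0.90111 × 0.99981 × 0.99993 = 0.8346.

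For H3, ln 2 / (1.1 × √(2/300)) = 7.72, so per-serotype power is Φ(7.72 − 1.96) > 0.9999 and H3 does not reduce the product. The asymptotic Farrington-Manning version gives 82.5%. Both agree with the plan's figure of about 83%.

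The plan already allows for 330 − 300 = 30 losses per arm. Assumed extra losses beyond that give:

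| Extra loss from 300 | PP n per arm | Power |
|---|---|---|
| 0 | 300 | 83.5% |
| 1% (3) | 297 | 82.9% |
| 3% (9) | 291 | 81.6% |
| 5% (15) | 285 | 80.7% |
| 20 infants | 280 | 79.7% |

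Power drops below 80% somewhere between 15 and 20 extra losses per arm. With the 30 already allowed, that is 45 to 50 of 330 (13.6% to 15.2%).

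**The case for a change.** The best case for acting is that sites and analysts do not read every section together. The Schedule of Activities sends sites to 6.5 for concomitant vaccines, and for vaccines other than influenza the timing sentence there gives only the limit after a dose; for influenza vaccine it gives both limits. The rescheduling rule for the starred exclusion criteria names Visit 1 only. No counting rule is stated for 27 or 28 days, and 9.5.1 uses the term prohibited vaccine without a cross-reference. Two people could classify the same infant differently, each citing the protocol, and the sSAP of October 2021 clarified its population definitions without touching this.

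All of that stands as criticism of the drafting. It does not show that the analysis goes wrong. The opening of 6.5 already supplies the missing limit by carrying forward the windows in 5.2, and those two sections together identify which vaccines are prohibited and when. Section 1.3 allows Visits 2 and 3 to run late. Cases that remain unclear go to the blinded deviation review, where exclusion is optional. The supportive Full Analysis Set, if that analysis is run, needs only the required doses and a serology result, so these deviations would not reduce it.

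**Conclusion.** No change to the analysis plan follows. The difference between 27 and 28 days is a clerical inconsistency between two descriptive sections and the schedule they rely on. The sentence in 6.5 is incomplete when read alone but is governed by the opening of its own section. The passages should be reconciled in wording; this review takes no position on which interval or vaccine timing is clinically right.

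Following the plan as written gives a sound primary result. The rules are the same in both arms and PP status is decided before unblinding, so no differential bias is shown. No stated figure is wrong. The possible harm is a modest loss of precision: from 83.5% to 80.7% power at the upper end of an assumed 1% to 5% extra PP loss. The documents give no basis for any particular share, so that range only illustrates the scale. The power figures also rest on the Table 5 rates, the 23F comparator, independence across serotypes and the unstratified form of the test.
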